5. RISKS AND BENEFITS OF THE DEVICE AND CLINICAL INVESTIGATION

5.1 Anticipated Clinical Benefits

The benefits of TransAeris stimulation in this subject population are unproven at this time although preliminary evidence suggests that a higher proportion of subjects will be weaned from MV by 48 hours with TransAeris therapy. Subjects may receive no direct benefits from study participation. It is possible that the use of TransAeris may result in the avoidance of prolonged mechanical ventilation due to VIDD, and reduction of MV-associated morbidity. The findings of this study are expected to benefit medical research and advance the development of TransAeris System, which would provide neuromuscular electrical stimulation to the diaphragm while the patient is on mechanical ventilation in the ICU to prevent, slow, or reverse diaphragm disuse atrophy and, more generally, to treat VIDD.

5.2 Anticipated Adverse Device Effects

The theoretical risks related to the study device are listed below, with the observed occurrence in the pilot study:

- Stimulus interferes with heart rhythm; 0 occurrences out of 10 patients
- Stimulus interaction with implanted cardiac defibrillator or cardiac pacemaker; 0 occurrences out of 10 patients
- Pain due to stimulation; 0 occurrences out of 10 patients
- Percutaneous electrode exit site infection requiring antibiotics; 0 occurrences out of 10 patients

The theoretical risks related to the procedure to insert or remove the TransLoc electrodes are listed below, with the observed occurrence in the pilot study:

- Bleeding during surgery due to insertion of the electrode; 0 occurrences out of 32 patients
- Tissue or organ damage during surgery due to insertion of the electrodes; 0 occurrences out of 32 patients
- Breakage of electrode lead; 0 occurrences out of 128 electrodes
- Accidental dislodgement of electrode from diaphragm; 1 occurrence out of 128 electrodes
- Unintentional device fragment retained after removal of electrode; 0 occurrences out of 108 removals
- Bleeding after removal of the electrodes; 0 occurrences out of 32 patients
- Exit site pain after removal of the electrodes; 0 occurrences out of 32 patients

5.3 Possible Interactions with Concomitant Medical Treatments

Warnings regarding possible interactions with other medical devices are included in the warnings section of the User Manuals (REF 77-1000-FR_B & REF 77-1002-FR_C) which is part of this investigational plan. In case of any identified or suspected interaction with other devices used in the care of the patient, the TransAeris stimulation will be ceased. If the interaction is verified, it will be noted as an adverse event, the TransLoc electrodes will be withdrawn and the patients' participation in the study will conclude.

5.4 Risk Mitigation Strategies

Stimulus interference with heart rhythm are mitigated in this protocol per study procedures sections 7.5.1.3.1 and 7.5.1.3.2 which describes cardiac rhythm monitoring. Pain due to stimulation is mitigated through device programming including programmable intensity and frequency settings and the optional burst mode as described in study procedures section 3.6.4.2. Percutaneous electrode exit site infection is mitigated by limiting TransAeris use to the hospital setting where proper exit site maintenance can be ensured. Infection is also mitigated by limiting the TransAeris stimulator to single patient use to prevent transmission of any bacterium from patient to patient on the device.

Additionally, procedure-related risks were mitigated through a prior feasibility study (IDE's G150040 & G170294) which investigated the safety and performance of the TransLoc electrodes including their insertion and removal and investigated the safety and performance of the TransAeris stimulation on open cardiac surgery patients. In total, 176 electrodes were successfully placed in 44 patients during these two pilot studies. Electrodes were placed concomitant to a primary surgical procedure done using one of three approaches: laparoscopic, open abdominal, and open chest. Electrode stability was demonstrated by the collection of daily diaphragm EMG readings. No unretrieved device fragments were left with the removal of electrodes. No device or procedure related adverse events from implantation through electrode removal were reported.

5.5 Risk to Benefit Rationale

Synapse applies the EN ISO 14971 standard for Risk Management in Medical Devices to evaluate identified risks, determine a risk rating and apply our risk acceptance policy. The procedures of analysis, as identified in our standard operating procedures for risk management, are kept up to date with findings from device performance in commercial use, as well as investigational use. Risk mitigation is performed through design practices, protective measures, or informational (instructions for use) with evaluation of these activities on at least an annual basis. An assessment of the detailed evaluation is performed by the Synapse management team and a determination is made if overall residual risk, after mitigation activities, is at an acceptable level. For this clinical investigation, the residual risks have been reviewed by the Synapse management team and the site investigators and determined that they are at an acceptable level. The potential benefits, while they may not apply directly to the individual patients in this study, outweigh the potential risks and the device is safe for human use in the context of the clinical investigation for the proposed intended use.

6. OBJECTIVES AND HYPOTHESES OF THE CLINICAL INVESTIGATION

6.1 Purpose

This study will be conducted as a randomized trial of the TransAeris system for the prevention and treatment of ventilator-induced diaphragm dysfunction (VIDD) in patients identified prior to surgery to be at greater risk of prolonged mechanical ventilation (MV).

6.2 Objectives

The specific objectives of this study are:

Primary objective:

- Evaluate the credibility of expected treatment benefits

Secondary objectives:

- Identify safety concerns
- Identify barriers to enrollment
- Evaluate the randomized protocol in single site setting, prior to multi-center expansion
- Assess the capability of collecting the specified evaluation criteria
- Assess the capability to quantify diaphragm electrical activity through diaphragm EMG monitoring

7. DESIGN OF THE CLINICAL INVESTIGATION

7.1 Type of Clinical Investigation

This study is a monocentric and open label randomized study in adult open cardiac surgery patients. Eligible patients from whom informed consent is obtained are enrolled in the study. All subjects will be implanted with the TransLoc electrodes during their primary surgery. Patients are randomized to treatment or control groups prior to surgical placement of the TransLoc electrodes.

7.2 Outcome Measures

7.2.1 Primary Safety Outcome

Incidence of serious device-related adverse effects

7.2.2 Primary Efficacy Outcome

Time on Mechanical Ventilation and Proportion of patients weaned at 48- and 120-hours post-op

7.2.3 Ancillary Outcomes

Safety:

Interference with ICU care
Device related adverse events
30-day mortality

Efficacy:

Time on mechanical ventilation,
(measured in hours from entry to ICU and reversal of paralytics)
EMG analysis of cross-over patients
Ventilator Free Days
Length of stay, ICU & Hospital

7.3 Investigational Devices and Comparators

Eligible patients from whom informed consent is obtained are enrolled in the study. All subjects will be implanted with the TransLoc electrodes during their primary surgery. Comparison will be made between treatment and control patients during the initial 120 hours of study, then comparison of cross-over control patients' EMG from baseline to treatment. Further comparison of MV Time, ventilator free days and other

outcome measures will be made for all patients, over the course of the 30-day treatment period, to literature on an observational basis.

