1. PROTOCOL SYNOPSIS

Title	Randomized Study of TransAeris® system for Enhanced Recovery After Surgery (ERAS) in cardiac surgery patients in France at risk of prolonged mechanical ventilation
Protocol Number	20-1000-108
Device Tested	TransAeris® System
Purpose	This study will be conducted as a randomized trial of the TransAeris system for the prevention and treatment of ventilator-induced diaphragm dysfunction (VIDD) in patients identified prior to surgery to be at greater risk of prolonged mechanical ventilation (PMV).
Study Objectives	
The specific objectives of this study are:
 
Primary objective:
 
• Evaluate the credibility of expected treatment benefits 
Secondary objectives:
 
• Identify safety concerns• Identify barriers to enrollment• Evaluate the randomized protocol in single site setting, prior to multi-center expansion• Assess the capability of collecting the specified evaluation criteria• Assess the capability to quantify diaphragm electrical activity through diaphragm EMG monitoring
Study Design	This study is an open label, randomized, cross-over study in adult open cardiac surgery patients. All subjects will receive TransLoc electrodes at the time of open sternotomy cardiac procedure. Half of subjects will have TransAeris turned on upon entry to ICU, the other half will receive standard of care with TransAeris turned on if still intubated on mechanical ventilation after 120 hours.

Outcome Measures	
Primary Safety: Incidence of Serious Device Related Adverse Events
 
Primary Efficacy: Mechanical ventilation time and proportion of patients weaned at 48- and 120-hours post-op
 
Ancillary Outcomes:
 
Safety:
 
 Interference with ICU care Device related adverse events 30-day mortality 
Efficacy:
 
 Time on mechanical ventilation 
 – measured in hours from entry to ICU and reversal of paralytics EMG analysis of cross-over patients Ventilator Free Days Length of stay, ICU & Hospital
Enrollment	30 subjects will be randomized prior to surgical placement of TransLoc electrodes
Participating Site	1 French site will participate in this study

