The prior pilot study of TransAeris (G170294) identified nine risk factors for PMV as an initial prognostic enrichment inclusion criterion. Based on the resulting MV use of 44 consented patients there were five risk factors identified to be the most significant criteria for determining PMV. They correctly identified 13 out of 14 patients (92.9%) that required PMV as the true positive patients that could potentially benefit from the TransAeris therapy. Conversely, the five risk factors identified 10 out of 29 patients (34.5%) not requiring PMV incorrectly as false positive patients. Defining the positive predictive value (PPV) as the true positive patients (n=13) out of the total positive (n=23) identifications results in a PPV of 56.5%. One additional modification, based on review by cardiac surgeons that participated in the study, the accepted categorization by the American College of Cardiology (ACC), and literature review, is to set the left ventricular ejection fraction (LVEF) accepted for inclusion risk to less than or equal to 30% (LVEF $\leq 30\%$). This is consistent with the ACC category of “Severe Dysfunction” and is the consistent with the LVEF levels discussed in Hessel, et.al.(12)

The Intervention is the application of the diaphragm stimulation in the enriched PMV population. Of course, to apply the TransAeris intervention, the TransLoc electrodes will have to be placed prophylactically at the time of cardiac surgery. This also reduces the risk of the intervention, as the 2015 feasibility (G150040) safety study showed that the TransLoc electrodes could be safely placed at the time of cardiac surgery, taking less than 5 minutes at the end of the procedure. The pilot study in cardiac surgery patients (G170294) also demonstrated 100% successful electrode removal. The electrodes were able to be removed fully intact in these studies and all other applications of the device, to date.

The Comparator in the model for efficacy in this study is twofold. The primary outcome of this study is to assess the prevention of VIDD through the difference in MV time and proportion of patients weaned at 48-

and 120-hours post-op between the treatment and control groups. The secondary outcome is to assess the treatment of VIDD by crossing over the control patients that remain on mechanical ventilation at 120 hours and observe if there is an effect on the ability to wean those remaining patients with stimulation.

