To assess the initial expected outcome, the observational pilot study of TransAeris, resulted in six patients weaned by 48 hours on MV, for a 60% proportion weaned. This compares 34.1% ($=1 - 65.9\%$) weaned from three recent datasets from Suarez-Pierre (2019), Hessels (2019) and the STS Adult Cardiac Database from July 2014 – June 2017.(12,13)

Table 1: Datasets of PMV patients

Dataset	Total Patients on MV		
	at 24 hours	at 48 hours	at 120 hours
Hessels (2019)	229	127 (55.5%)	Not reported
Suarez-Pierre (2019)	1698	1024 (60.3%)	494 (29.1%)
STS (2014 – 2017)	109,380	72,240 (66.0%)	38,120 (34.9%)
TOTAL	111,307	73,391 (65.9%)	38,614 (34.8%)

To power a pivotal study for a 20% risk reduction (RR) in the pivotal study, we would need a total of ≈ 192 patients randomized. Where the RR is calculated as:

$$\begin{aligned} RR &= 20\% = [\text{Control On MV at 48hrs} - \text{Treatment on MV at 48hrs}] \\ &= 65.9\% - 45.9\% \end{aligned}$$

Thus, both groups would have the same rate of patients that would wean prior to 24 hours, based on the prognostic enrichment inclusion criterion, of 43.5% ($= 1 - \text{PPV}$). The TransAeris stimulated group would be anticipated to have 46% of the PMV group still on MV at 48 hours and the control group to have 66% on MV at 48 hours. In the observational pilot we saw 40% on MV at 48 hours. This would translate, in a 40-patient study, to 4 to 5 treatment patients on MV and 6 to 7 control patients on MV at 48 hours. While still anticipated to be statistically inconclusive, with the small sample size requested, as a next step this single-site randomized study is expected to lead into the total 340 implanted patients to yield 192 PMV sample multi-center pivotal study. That is derived from the target 192 patients with PMV and 56.5% positive prediction rate requiring a pool of 340 enrolled patients implanted.

A secondary comparator is to the STS adult cardiac dataset reported number of the enriched PMV group reaching 5 days of MV. As discussed above, we would expect 35% of those patients to still need MV at 5 days. Thus, in a set of 15 control patients, we would expect 2 to 3 patients to still be on MV at 5 days.

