7.4.2 Point of Enrollment

30 subjects will receive TransLoc electrodes. Subjects from whom informed consent is obtained are enrolled in the study. Subjects will be randomized to:

Group 1: Tx (Treatment with TransAeris stimulation upon completion of procedure), or;

Group 2: SOC (Control with cross-over to Treatment if still on MV at 120 hours post-op).

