7.5.1.3.2 Standard of Care (SOC) Group

The SOC group does not receive TransAeris stimulation for the first 120 hours of mechanical ventilation. SOC group patients will not be stimulated unless they are still on mechanical ventilation at 120 hours, at which point they will have an EMG recording made on the case report form, page 6. If intact bilateral EMG is not observed a competing event will be recorded on the competing event case report form, page 10. Otherwise the patient will be identified as a Cross-over patient on the daily post-op case report form, page 5, and follow the process for the Tx group as identified in section 7.5.1.3.1, with the start of TransAeris stimulation.

Any device deficiencies or competing events, that would inhibit or preclude weaning, should be indicated on the daily post-op case report form and the associated detail case report form for device deficiencies, page 12, or competing events, page 10, should be completed for all patients, Tx, SOC or cross-over.

A final EMG recording will be performed prior to electrode removal in all patients. Recordings will be made for a period of at least one minute during quiet, resting breathing or quiet, mechanical ventilation support.

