8. STATISTICAL CONSIDERATIONS

8.1 Study Design and Statistical Objective

This study is designed to gather data on the use of TransAeris in subjects identified prior to surgery to be at greater risk of prolonged mechanical ventilation after surgery. Data collected will be compared qualitatively to the relevant clinical literature and used to inform the design and statistical parameters for a subsequent multi-center pivotal trial.

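### For the 30-day outcomes the plan names published literature as the only comparator, although a randomised control arm is available

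*Combined protocol and SAP*

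**What the plan says.** Section 7.3 sets out three comparisons. The first is between arms and has a time limit: "Comparison will be made between treatment and control patients during the initial 120 hours of study". The second is within patient, on the EMG of controls who cross over. The third takes MV time, ventilator-free days and other "outcome measures will be made for all patients, over the course of the 30-day treatment period, to literature on an observational basis".

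The statistical section does not add to this. Section 8.1 states: "Data collected will be compared qualitatively to the relevant clinical literature". Section 8.4.3 defines mortality through 30 days, MV time to successful wean, ventilator-free days to day 28, and hospital and ICU stay. It says they will be reported descriptively, without saying whether by arm or for the whole group.

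Between-arm comparison is specified in two other places. Section 4.2 specifies it for the primary efficacy outcome (MV time and proportion weaned at 48 and 120 hours). Section 7.5.1.7 specifies it for adverse events, with no 120-hour limit.

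**The concern.** The primary objective is to judge whether the expected treatment benefit is credible, and the data are meant to shape a pivotal trial. For total MV time, ventilator-free days and length of stay, the plan turns to an external comparator when a concurrent randomised one exists. That raises two problems.

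- **Mixed exposure.** The set of all patients contains people stimulated from ICU entry, people stimulated only from 120 hours, and people never stimulated. A single summary of that set describes neither the device nor standard care.
- **Different population.** The published cohorts in Table 1 consist of patients already on MV at 24 hours. This trial enrols before surgery on risk factors and expects a large share to wean before 24 hours. A comparison that ignores this can show a benefit when the device does nothing.

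At stake is whether the 30-day results can inform the pivotal design at all.

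**Working it through.** **Inputs**
- Section 7.4.2: "30 subjects will receive TransLoc electrodes". Synopsis: "Half of subjects will have TransAeris turned on upon entry to ICU". Hence 15 per arm.
- Section 7.5.1.3.2: "SOC group patients will not be stimulated unless they are still on mechanical ventilation at 120 hours".
- Section 4.2: the five risk factors give 13 true positives among 23 positives, which "results in a PPV of 56.5" per cent. The other 43.5% are expected to wean before 24 hours, at the same rate in both arms.
- Section 4.2, on the group with prolonged MV (PMV, at least 24 hours): "we would expect 35% of those patients to still need MV at 5 days". Table 1 gives 34.8%.
- Section 4.2: 65.9% of PMV controls on MV at 48 hours against 45.9% hypothesised with treatment, a 20-point effect.

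**1. The plan's own cross-over figure.** Section 4.2 expects 2 to 3 of 15 controls on MV at 5 days. 15 × 0.565 × 0.348 = 2.95; with 35% it is 15 × 0.565 × 0.35 = 2.97. Both agree. Without the PPV, 15 × 0.35 = 5.25 does not, so the plan applied the PPV.

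**2. Composition of the set of all patients.** Never-stimulated controls: 15 − 3 = 12 to 15 − 2 = 13, that is 12/30 = 40% to 13/30 = 43%. At most 15 + 2 = 17 to 15 + 3 = 18 are ever stimulated. This is an upper bound, since a treatment patient who weans before stimulation starts is also unstimulated.

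**3. Effect if all patients are taken as one group.** I use 48 hours because it is the only outcome for which the plan gives both a control rate and an effect; that outcome itself keeps its between-arm comparison. Among PMV patients with equal arms: (65.9% + 45.9%)/2 = 55.9%. Against 65.9% in the literature the difference is 10.0 points, half of the 20 hypothesised. No control is stimulated before 120 hours, so cross-over plays no part in this figure.

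**4. Population mismatch, if Table 1 is the comparator.** With no device effect, the proportion of all enrolled patients on MV at 48 hours is 0.565 × 65.9% = 37.2%. Against 65.9% that is an apparent benefit of 28.7 points, more than the 20 points sought for the pivotal trial.

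**5. Both together.** With the full hypothesised effect, the single-group figure is 0.565 × 55.9% = 31.6%. It differs from the null figure in step 4 by only 0.565 × 10.0 = 5.65 points. The literature comparison would look strongly favourable in either case and would hardly tell the two apart.

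**6. What the by-arm comparison offers.** For a standardised mean difference at 15 versus 15, the 95% half-width is 1.96 × √(2/15) = 0.72 SD. For the 48-hour proportion among all patients (37.2% against 0.565 × 45.9% = 25.9%, difference 11.3 points) it is 1.96 × √(0.372 × 0.628/15 + 0.259 × 0.741/15), about 33 points. The documents give no SD for ventilator-free days, MV time or stay, so nothing can be computed on those scales.

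**The case against.** The best defence is that the literature comparison is labelled further, observational and qualitative, in a 30-patient study without planned hypothesis tests. Nobody is proposing to claim efficacy from it. Much of this stands, and it rules out several stronger readings.

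- A reader might infer that the randomised control arm is discarded. It is not. It is kept for the primary efficacy outcome to 120 hours and for adverse events, and the literature comparison is additional. Deaths reported as serious adverse events fall within the adverse-event comparison, although 30-day mortality as an endpoint is not named there.
- A reader might take pooling as settled. Reference to all patients may mean one group, or both arms shown separately. Sections 7.3 and 8.4.3 do not decide it, and a by-arm display is not excluded.
- A reader might think that literature takes over only after 120 hours. Section 7.3 places that comparison over the whole 30-day period.
- A reader might take the ever-stimulated share (17 to 18 of 30, about 60%) as the fraction of effect that survives. That would count controls crossed over at 120 hours as if stimulated from ICU entry. The plan gives no effect for delayed stimulation, so no dilution factor can be derived beyond 48 hours.

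It is also fair that sections 7.3 and 8.1 do not name the literature to be used, that Table 1 has no ventilator-free days, stay or mortality, and that section 4.2 itself allows for early weaners when it projects numbers. Nor is the by-arm contrast perfect: the trial is open label, and section 7.4.4 withdraws and replaces patients not implanted after randomisation.

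None of this supplies the missing comparison. Even with results shown by arm, the only comparator named for these outcomes is external.

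**Conclusion.** The point holds as a poor choice of comparator for secondary outcomes. It is not a failure of the primary analysis. No section specifies a between-arm comparison of ventilator-free days, total MV time, ICU or hospital stay, or 30-day mortality as an endpoint. The randomised contrast answers the question better and needs no further data.

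The 40% to 43% never-stimulated share rests only on the plan's own figures. The reduction from 20 to 10 points is conditional on treating all patients as one group. The 37.2% against 65.9% is conditional on Table 1 being the comparator and on all enrolled patients being set against it. Both are illustrated at 48 hours; the size of the distortion on the 30-day scales cannot be computed.

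Cross-over is no reason to avoid the by-arm comparison. It is expected in about 3 of 15 controls (20%) and only from 120 hours. It changes the contrast to immediate versus delayed-or-no stimulation, which remains interpretable.

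**What to change.** In sections 7.3 and 8.4.3, state that ventilator-free days to day 28, total MV time, 30-day mortality, and ICU and hospital stay will be reported by randomised arm, as randomised, with the between-arm difference and 95% CI. Label the contrast immediate versus delayed-or-no stimulation, and label the result as estimation only, given 15 versus 15.

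Keep the literature comparison as supplementary context. Name the sources, show each arm separately, and restrict to patients with at least 24 hours of MV where the published cohort is defined that way. Being on MV at 24 hours is determined after randomisation, so that subset should serve only the literature comparison and should not replace the as-randomised one.

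The cost is wording and one by-arm table from data already collected. No hypothesis test, extra patient or new assessment is needed, and the descriptive character of the plan is unchanged.
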